#### 5.2.2. Preparation and Administration

Visually inspect drug product solution for particulate matter and discoloration prior to administration. OPDIVO is a clear to opalescent, colorless to pale-yellow solution. Discard the vial if the solution is cloudy, is discolored, or contains extraneous particulate matter other than a few translucent-to-white, proteinaceous particles. Do not shake the vial.

#### 5.2.3. Preparation

Vials of 100mg will be provided. There are 5 vials per carton. Withdraw the required volume of nivolumab and transfer into an intravenous container. Dilute nivolumab with either 0.9% Sodium Chloride Injection, USP or 5% Dextrose Injection, USP, to prepare an infusion with a final concentration of 1-10 mg/mL, with a maximum total volume of 160 mL for prepared infusions (including overfill). Mix diluted solution by gentle inversion. Do not shake. Discard partially used vials or empty vials of nivolumab.

#### 5.2.4. Storage of Infusion

The product does not contain a preservative.

After preparation, store the nivolumab infusion either:

- at room temperature for no more than 8 hours from the time of preparation. This includes room temperature storage of the infusion in the IV container and time for administration of the infusion or
- under refrigeration at 2°C to 8°C (36°F-46°F) for no more than 24 hours from the time of infusion preparation.

Do not freeze.

### 5.2.5. Administration

Administer the infusion over 60 minutes through an intravenous line containing a sterile, non pyrogenic, low protein binding in-line filter (pore size of 0.2 micrometer to 1.2 micrometer). Do not coadminister other drugs through the same intravenous line. Flush the intravenous line at end of infusion.

### 5.3. Capecitabine

Capecitabine will be given at 1250 mg/m^2 PO BID for Days 1-14 only of a 21-day cycle for 6 cycles.

Commercially available capecitabine will be used. Locally obtained commercial supplies of capecitabine will be used in accordance with local regulations. As capecitabine is an oral drug available in fixed doses, the dose administered may not exactly match the calculated dose. Determination of the rounding of capecitabine doses for administration should be made according to local institutional practices, with documentation of both the calculated and administered dose. Per package insert, it is recommended that capecitabine be administered with food. Capecitabine should be stored according to the package insert. For capecitabine, the package insert and local standard of care rules for dose reduction should also be applied. Dose modifications will be documented.

#### 5.3.1 Dose modifications for capecitabine for clinical adverse events considered related to capecitabine

CTCAE Toxicity Grades	During a course of therapy	Dose adjustment for Next Treatment (% of starting dose)
Grade 1	Maintain dose level	Maintain dose level
Grade 2		
1 st appearance	Interrupt until resolved to Grade ≤ 1	100%
2 nd appearance	Interrupt until resolved to Grade ≤ 1	75%
3 rd appearance	Interrupt until resolved to Grade ≤ 1	50%
4 th appearance	Discontinue permanently	NA
Grade 3		
1 st appearance	Interrupt until resolved to Grade ≤ 1	75%
2 nd appearance	Interrupt until resolved to Grade ≤ 1	50%
3 rd appearance	1	NA

	Discontinue permanently	
Grade 4 1 st appearance	Discontinue permanently	NA

## 6.0 STUDY PROCEDURES AND TREATMENT ASSIGNMENT

### 6.1. Table of events

	Pre-registration	Screening	On Study (maximum 6 cycles; cycle is every 21 d)	Treatment discontinuation	Surveillance
	Post-surgery	-30 days	D1 of each cycle +/- 7 days. Each cycle is 21 days.	30 days (+/-7 days) after last dose	
Assessments					
Informed consent	X				
Medical history and height		X			
Physical examination		X	X ^	X	
Weight, BP		X	X ^	X	
ECOG PS		X	X ^	X	
CMP		X	X	X	
Creatinine clearance		X	X	X	
CBC with differential		X	X	X	
Breast imaging (remaining tissue only)					Yearly +/- 30 days
Adverse event and con meds assessment		X	X ^		
Urine pregnancy or serum HCG for WOCBP only		X	X ^ (every 3 weeks) for Arm A and C		
ACTH and Thyroid Function Tests#		X	X ^ (week 12) for Arm A and C	X	
Hepatitis and HIV screening*		X			
EORTC QLQ-C30 &		X	X (week 6)	X	
Telephone communication or focused physical exam+					Every 3-6 months
Treatment					
			Nivolumab 360mg iv q3w; capecitabine 1250mg/m  D1-14		

Correlative Samples					
Tumor from initial diagnosis		X (if available)			
Tumor from definitive surgery – with IHC testing for MSI	X				
Serum for peripheral immunoscore			X ^ (baseline, week 6 and 12)	X (if recurrence)	
Blood for ct-DNA \$			X ^ \$ (baseline, week 6 and 12)	X (if recurrence)	
Tumor from metastatic site				X (if recurrence)	

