### 1.4. Evaluating anti-tumor immunity in the absence of measurable disease

A significant challenge in evaluating the effects of experimental adjuvant therapies is the lack of measurable disease to assess therapeutic effects. In this setting, when tumor is not detectable such as in patients with early BC who have undergone surgical resection of their tumor, the identification of biomarkers in the peripheral blood – the most readily available tissue for sampling – to assess effects of the intervention is intuitively attractive. Immune cell subsets within peripheral blood mononuclear cells (PBMC) have been analyzed to determine if a peripheral immunoscore could have any prognostic significance for patients undergoing immunotherapy. Although to date there is no validated FDA-approved circulatory immunological biomarker for patients with breast cancer, the refined peripheral immunoscore (PIS) defined by

Criterion 1: Classic cell types		Criterion 2: Phenotypes of refined cell subsets reflecting immune function		
Description	Expected effect on PFS	Description	Expected effect on PFS	Reference
% CD4	Positive	% Central memory CD4 hi	Positive	(9)
		% CD4 expressing ≥2 suppressive markers 	Negative	(20, 21)
% CD8	Positive	% Central memory CD8 hi	Positive	(9)
		% CD8 expressing ≥2 suppressive markers 	Negative	(20, 21)
% Treg 	Negative	% Treg CD45 lo	Negative	(22, 23)
% MDSC 	Negative	% MDSC Lin  	Negative	(24, 25)
% NK 	Positive	% NK CD56 hi CD16 +	Negative	(26, 27)
Ratio CD4:Treg	Positive	Ratio central memory  CD4:Treg CD45 lo	Positive	
Ratio CD8:Treg	Positive	Ratio central memory  CD8:Treg CD45 lo	Positive	
Ratio CD4:MDSC	Positive	Ratio central memory  CD4:MDSC Lin 	Positive	
Ratio CD8:MDSC	Positive	Ratio central memory  CD8:MDSC Lin 	Positive	
		Ratio central memory  CD4:NK CD56 hi CD16 +	Positive	
		Ratio central memory  CD8:NK CD56 hi CD16 +	Positive	

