NOTE: Frequencies of PBMC subsets represented as a percentage of total PBMCs.  CD45RA+CCR7+;  CTLA-4, PD-1, Tim-3, 2B4;  CD4+CD25+FoxP3+CD127;  CD3CD16CD19CD20^-CD56CD33HLA-DR^-HLA-DR^-HLA-DR^-;  CD14+CD15+;  CD3CD56.

Table 1. Refined peripheral immunoscore

Farsaci et al (Table 1) was validated in a group of patients with metastatic BC receiving docetaxel and immunotherapy, and shown to be predictive of progression free survival (PFS). When compared to predefined analyses of "classic" immune cell types (CD4, CD8, natural killer cells, regulatory T cells, myeloid-derived suppressor cells, and ratios) that revealed no differences in PFS for either arm

(docetaxel alone or docetaxel with vaccine), predefined analyses of refined immune cell subsets for which a biologic function had been previously reported revealed statistically significant improved PFS ( $P < 0.001$ ) for those receiving docetaxel plus immunotherapy (Fig 2). Based on these results, we selected for our study the PIS as a surrogate of clinical benefit and a new strategy to identify patients with BC who may benefit from immunotherapy to eliminate residual micrometastasis.

[figure not shown]
[figure not shown]

Figure 2.a Docetaxel alone

Figure 2.b Docetaxel and vaccine

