#### **4.1.2 Number of Subjects**

45 patients will be enrolled with advanced triple negative breast cancer. Patients who don't have evaluable samples as per protocol will be replaced.

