#### **6.6. On Treatment**

Blood samples will be obtained for correlative studies on week 6 and 12 (see Correlative Laboratory Manual for more details).

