## **8.4 Endpoints**

### **8.4.1. Primary Endpoint**

a. Quantification of immune activation measured by changes of PIS from baseline to week 6 in each arm.

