## **9.0 CORRELATIVE RESEARCH**

### **9.1 Peripheral Immunoscore**

We selected the refined PIS as a surrogate of clinical benefit and a new strategy to identify patients with TNBC and high-risk disease who may benefit from immunotherapy to eliminate residual micrometastasis. The peripheral immunoscore was calculated based on a predefined analyses of refined immune cell subsets for which a biologic function had been previously reported revealed statistically significant improved PFS ( $P < 0.001$ ) in patients with metastatic breast cancer receiving docetaxel plus immunotherapy compared to docetaxel alone (Fig 2). To calculate the PIS, flow cytometry was performed on PBMC harvested at different time points. A multiparametric flow cytometry platform was applied to measure the frequency of PBMC. Patients' PBMCs by density gradient separation, and then 1 mL of PBMCs was cryopreserved in liquid nitrogen at a concentration of 107 cells/mL per vial. On the day of staining, one vial of cryopreserved PBMCs per patient was defrosted, cells were counted, and then stained with the appropriate monoclonal antibodies. Table 1 shows the classic immune cell types as well as those refined subsets with a phenotype reflecting immune function. Viability of all samples following thawing after cryopreservation was 80% to 95%. The frequency of individual subsets was calculated as a percentage of total PBMCs to help reduce the bias that could occur in the smaller subpopulations with fluctuations in parental leukocyte populations. The PIS defined by Farsaci et al was selected based on being the closest to the particular scenario proposed on the OXEL study. This has been validated in a group of patients with metastatic BC receiving docetaxel and immunotherapy, and shown to be predictive of PFS. While this (and other) immune biomarkers in the blood available today have not been validated in all clinical scenarios – including early BC – available data suggests that this immunoscore constitutes a promising surrogate marker of clinical outcome in this group of patients. The PIS will be performed 40) at [name] lab at NIH, which developed this particular immunoscore.

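### The table of events names serum as the specimen for the peripheral immunoscore, but the protocol defines that score on blood mononuclear cells, which serum does not contain

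*Combined protocol and SAP*

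**What the plan says.** In the correlative-samples block of the table of events (section 6.1), the PIS row reads "Serum for peripheral immunoscore". It is scheduled at baseline, week 6 and week 12, and again if disease recurs.

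The score itself is described as follows:

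- Section 1.4 introduces it through cells: "Immune cell subsets within peripheral blood mononuclear cells (PBMC) have been analyzed to determine if a peripheral immunoscore could have any prognostic significance".
- The note under Table 1 gives the unit of the components: "Frequencies of PBMC subsets represented as a percentage of total PBMCs".
- Section 9.1 gives the method: "To calculate the PIS, flow cytometry was performed on PBMC harvested at different time points". It then describes density-gradient separation and freezing, after which "one vial of cryopreserved PBMCs per patient was defrosted, cells were counted, and then stained with the appropriate monoclonal antibodies".

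Section 8.4.1 makes this score the primary endpoint: "Quantification of immune activation measured by changes of PIS from baseline to week 6 in each arm".

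The other collection instructions do not name a specimen beyond blood. Section 6.6 reads "Blood samples will be obtained for correlative studies on week 6 and 12 (see Correlative Laboratory Manual for more details". Section 6.5 is similar for day 1, and section 6.8 groups the PIS with ct-DNA as blood correlatives at recurrence. Section 9.3 also sends the reader to the laboratory manual for handling and processing.

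**The concern.** Of the places in the protocol that mention PIS sampling, the table of events is the one that sets out what is taken and when. For the assay behind the primary endpoint it names a fraction of blood that holds no cells.

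The primary endpoint is a within-patient change, so it needs two usable samples, at baseline and at week 6. If either is processed as serum, that patient has no primary-endpoint value. The baseline sample matters most. It cannot be replaced by a later draw once treatment has started, and it is also the reference for the week 12 change (section 8.4.2, item a) and for the association of PIS change with distant recurrence-free and overall survival (item c).

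**Working it through.** The plan states no figure on this point, and no sample size, power or rate enters it. The check is a comparison of the passages.

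**1. What the score needs.** Table 1 lists percentages of cell types and refined subsets, and ratios between them. Its note sets total PBMC as the denominator. Section 9.1 has the cells separated, frozen, thawed, counted and stained. Every input is a cell count or a ratio of counts.

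**2. What the schedule supplies.** Serum is what remains after blood has clotted and the cells have been removed. This is general laboratory knowledge applied to the protocol's own definition. With no PBMC present, both the numerators and the denominator of the Table 1 components are unobtainable.

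**3. Whether serum is loose wording for blood.** The next row of the same table gives the ct-DNA specimen as blood, and the pregnancy-test row uses serum in its ordinary sense. The table therefore distinguishes the two words, and a coordinator could fairly read the PIS and ct-DNA rows as different specimens. The footnotes to the table that touch the correlative samples concern timing and an optional ct-DNA draw. None redefines the PIS specimen.

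**4. Whether another part of the protocol corrects the row.**

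- Sections 6.5, 6.6 and 6.8 say blood without naming a fraction. They are compatible with whole blood for PBMC, but do not state it.
- The banking objective in the synopsis and in section 8.1 lists plasma and PBMC, not serum. This shows that PBMC were expected to exist, but the table of events has no row for collecting them.
- Section 9.1 is largely in the past tense, as an account of the source assay. It is nevertheless the protocol's only description of how the PIS is calculated, and it closes by saying that the PIS will be performed by the laboratory that developed it.
- No part of the protocol describes a serum-based PIS.

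**5. Which scheduled samples are affected.** The row covers three scheduled time points plus recurrence. Two of the three, baseline and week 6, feed the primary endpoint. Baseline and week 12 feed the secondary PIS endpoint.

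The row contradicts the definition of the score. The rest of the protocol points to PBMC, but no sentence tells sites to draw blood for PBMC isolation.

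**The case against.** The strongest reply is that the row is a label and not a processing instruction. It gives no tube, volume, spin or storage condition. Sections 6.5, 6.6 and 9.3 leave those to the Correlative Laboratory Manual, and a laboratory that developed the score would be expected to ask for the cells it needs. On this view one stray word stands against sections 1.4, 6.8, 8.1 and 9.1, and nobody would have acted on it.

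Much of that stands. The manual is not in these documents and may name the right specimen, so the harm is conditional on a site taking the row literally.

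Three stronger conclusions might be drawn, and the documents support none of them:

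- **That samples were taken as serum and the endpoint was lost.** Nothing in the documents shows what was collected.
- **That each error costs one patient in an arm of 15.** That is only arithmetic on the arm size. There is no probability of error to attach to it, and section 4.1.2 says "Patients who don't have evaluable samples as per protocol will be replaced", so the evaluable count would be restored rather than reduced.
- **That the row itself takes randomised patients out of the comparison.** Replacement after randomisation comes from sections 4.1.2, 4.6.2.1 and 8.5.1. It would operate in the same way with the row worded correctly, and is a separate matter.

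What the reply does not remove is the error in the schedule. If the manual asks for PBMC, two documents that sites work from disagree on the specimen for the primary endpoint. If it repeats the table, the error is carried into practice.

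**Conclusion.** The point holds as an internal inconsistency: the section 6.1 row is wrong as written. It names a specimen from which the primary endpoint cannot be obtained, and it conflicts with section 1.4, the note to Table 1 and section 9.1. It is not a choice of design, since nothing in the protocol argues for a serum measure.

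The consequence can be stated only per sample. A visit sampled as serum yields no PIS, and a missing baseline or week 6 value means no primary-endpoint value for that patient. How often that could have occurred cannot be estimated from the documents, and it may be never.

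The conclusion rests on two things: that section 9.1 describes the assay the trial will use, which its closing sentence supports, and that serum is meant in its usual sense, which the rest of the table supports. It should be corrected because the row governs the primary endpoint at several sites and the correction costs almost nothing.

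**What to change.** In section 6.1, change the PIS row to: *Whole blood for PBMC isolation (peripheral immunoscore)*. Leave tube type, volume and processing to the Correlative Laboratory Manual, but check that the manual names the same specimen and that both agree with section 9.1. In section 9.1, add one sentence in the future tense saying that PBMC will be isolated from blood drawn at baseline, week 6 and week 12, and at recurrence.

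If sampling has already taken place, confirm from the specimen records what was collected at each visit, and report any visit without PBMC as a missing PIS value.

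The cost is one table row, one sentence and a check against the manual, plus a records check if samples already exist. No visit, blood draw or procedure is added.

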# Thyroid-stimulating hormone (TSH); free T3 and free T4 at screening and reflex when TSH is abnormal at subsequent visits

\* hepatitis B surface antigen, anti-HBc, anti-HBs, hepatitis C antibody (if hep C Ab is positive, reflex to Hep C RNA) or hep C RNA, HIV-1 and -2 antibody (testing for HIV-1 and HIV-2 must be performed at sites where mandated by local requirements)

\$ there will be an **optional draw** for ct-DNA 24-48h after the first drug administration

^ +/- 7 days. If a cycle is delayed due to blood counts, no need to repeat physical exam and correlative samples. The correlatives should follow C1D1 as baseline whenever possible and not be delayed in case of delays in treatment.

+ Every 3 months +/- 30 days for the first 2 years, then every 6 months +/- 30 days in year 3

& EORTC QLQ-C30 questionnaires to be completed at screening, week 6 and end of treatment

## **6.2. Pre-registration**

Participants who sign informed consent will be pre-registered and tissue from surgery will be requested. Once confirmed availability and sufficient material, patients will undergo screening materials.

## **6.3. Screening**

Within 30 days of study registration:

- Complete medical history and complete physical examination including: height, weight, BP and ECOG performance status
- Complete metabolic profile including serum chemistries and electrolytes
- Calculated creatinine clearance
- Complete blood count with differential
- Urine pregnancy test or serum HCG (only in women of child bearing potential, WOCBP) within 24 hours prior to the start of nivolumab. Women should be counseled regarding acceptable birth control methods to utilize from the time of screening to start treatment. In addition, women of child bearing potential must accept to have a pregnancy test every 3 weeks if they are randomized to a nivolumab arm.
- Adverse event and concomitant medication assessment

- EORTC QLQ-C30 should be completed during screening
- Obtain tumor from definitive breast surgery (mandatory) and from initial biopsy (if tissue is available) and send to the main site (Georgetown). See lab manual for more details.

**Note:** Assessments performed for clinical indications (not exclusively to determine study eligibility) may be used for screening/baseline values even if the studies were done before informed consent was obtained.

#### **6.4. Randomization**

Eligible patients will be randomized to one of three arms (see 8.3.)

#### **6.5. On Study Day 1**

Cycle 1 Day 1 testing need not to be repeated if completed within 14 days of starting therapy. Will be obtained blood samples for correlative studies (see Correlative Laboratory Manual for more details). Cycle 1 Day 1 must occur within 2 weeks after receiving randomization results.

#### **6.6. On Treatment**

Blood samples will be obtained for correlative studies on week 6 and 12 (see Correlative Laboratory Manual for more details).

#### **6.7. Treatment discontinuation**

A participant will be discontinued from the protocol therapy under the following circumstances:

- if there is evidence of progressive disease
- if the treating physician thinks a change of therapy would be in the best interest of the participant
- if the participant withdraws consent to protocol treatment
- if the drug exhibits unacceptable adverse events. Participants will be followed until the resolution of these adverse events.
- if a participant becomes pregnant

Patients may temporarily suspend study treatment if they experience an adverse event that requires a dose to be held. If study treatment is held because of adverse events for > 42 days beyond what was planned, then the patient will be discontinued from any study drug and be followed for safety. If, in the judgment of the investigator, the patient is likely to derive clinical benefit from resuming nivolumab and/or capecitabine after a hold > 42 days, study drug may be restarted with the approval of the Medical Monitor.

Dose interruptions for reason(s) other than adverse events, such as surgical procedures, may be allowed with Medical Monitor approval. The acceptable length of interruption will depend on agreement between the investigator and the Medical Monitor.

After treatment discontinuation, in the event of a continuing AE, patients must be followed up until resolution or stabilization of the AE.

### **6.8. Surveillance**

Participants will be monitored by their treating physicians for the development of either local (chest wall, axillary, or supraclavicular nodes) or distant recurrent disease, and survival, at least once every 3 months for the first two years, then at least every 6 months during year 3. Surveillance will be done through telephone communication, focused physical exam or review of medical records. Surveillance for immune-related adverse events will be included in these follow up visits or telephone calls. The Principal Investigator will notify the Data Safety Monitoring Board of any serious adverse events and immune related adverse events that are believed to be related to prior drug treatment or study procedures that occur at any time after a patient has discontinued treatment.

For those patients that develop a recurrence while on active treatment or during the follow up period (i.e. 3 years), blood correlatives (ctDNA and PIS) and tissue biopsy will be obtained. Tissue for research will only be requested (one block or 13 unstained slides) if a biopsy is done as part of routine care, either to confirm metastatic disease and/or to repeat markers.

